3.4.1 Anti-S Protein IgG Serology Subset

All participants in each PP Analysis Set who are tested for anti-S protein IgG antibodies using ELISA prior to study vaccination will be included in this subset.

3.4.2 Neutralization Assay Subset

All participants in each PP Analysis Set who are tested for neutralizing antibodies prior to study vaccination will be included in this subset.

3.4.3 hACE2 Receptor-Binding Inhibition Assay Subset

All participants in each PP Analysis Set who are tested for ACE2 receptor-binding inhibition antibodies prior to study vaccination will be included in this subset.

3.5 Discussion of Populations to be Used for Various Analyses

All selected participants will be used for subject disposition. Demographic data and other baseline data will be based on Safety Analysis Set and both PP Analysis Sets. Besides safety AE summaries, prior and concomitant medications, medical history, and protocol deviations, physical examination will be based on the Safety Analysis Set. Immunogenicity summaries and associated statistical analyses will be based primarily on both PP Analysis Sets (PP1 and PP2).

3.5.1 Protocol Deviations

A protocol deviation is any change, divergence, or departure from the study design or procedures defined in the protocol. An important deviation (sometimes referred to as a major or significant deviation) is a subset of protocol deviations that leads to a participant being discontinued from the study or significantly affects the participant's rights, safety, or well-being and/or the completeness, accuracy, and reliability of the study data. An important deviation can include nonadherence to inclusion or exclusion criteria or nonadherence to regulatory authority including ICH E6(R2) guidelines.

Protocol deviations will be documented by the clinical monitor throughout the course of monitoring visits. The investigator will be notified in writing by the monitor of deviations. The IRB should be notified of all protocol deviations, as appropriate, in a timely manner.

Some PDs may be determined programmatically through the course of the trial. Syneos ensures these are reconciled with manually determined PDs in Syneos's CTMS (clinical trial management system). Examples of programmatically determined PDs are provided in [Table 4](#).

Table 4: Programmatically Determined Protocol Deviations

Inclusion/Exclusion Criteria Not Met
Missed Visit or Blood Draw
Out of Window Visit or Blood Draw
Trial Procedure Not Done

Review and categorization of protocol deviations will occur prospectively during the study prior to database freeze or lock(s). The PD listing collected by Syneos CTMS suitable for import for SAS will provide the category of protocol deviation and the corresponding description of each protocol deviation, with a flag to indicate if a deviation was recommended by Syneos to consider as major or minor.

3.5.2 Major Protocol Deviations Assessment

Protocol deviations deemed to indicate clear violations of GCP and/or subject consent; or to have a likely effect on the primary and secondary immunogenicity outcomes will exclude those participants from both PP analysis sets (PP1 and PP2). This determination will be made by the NOVAVAX Clinical Lead prior to database freeze or lock.

When interim analysis (Day 29 primary analysis) DB freezes or Day 181 final analysis DB locks, Syneos will assess protocol deviations and create a consensus final protocol deviations assessment file. NOVAVAX team will determine whether PDs are major and make the final decision of which participants will be excluded from the PP analysis based on the PD listing from Syneos.

In general, inclusion/exclusion criteria failure, receipt of prohibited therapies, receipt of another COVID vaccine (authorized or approved), missed blood draw and laboratory samples obtained sufficiently outside visit windows to likely impact the result will be deemed “major” deviations relevant for analysis. Criteria for this determination will be established prior to review of PDs. Any positive PCR or anti-NP result obtained at baseline Day 1 is not exclusionary and will not be considered a major PD.

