As the 3rd secondary objectives of characterizing the cross-reaction of neutralizing and IgG antibodies induced by the ancestral strain Novavax vaccine to more recent SARS-CoV-2 variants and any other variants for which appropriate assays are available, the derived/calculated endpoints of Nab response for **the group receiving updated Novavax COVID-19 Vaccine based on recent variant(s)** will include Nab GMTs at Days 1 and 29, $GMFR_{Post/Pre}$ (Day 29 vs. Day 1), $GMR_{312/307}$, SCRs (Day 29 vs. Day 1), and difference in SCRs ($SCR_{312} - SCR_{307}$) in Nab titers to be calculated using the same calculations and comparison periods as noted above for **the group receiving ancestral strain Novavax vaccine**.

Above parameters based on the Pseudovirus-based Nab response per Wuhan strain from Study 2019nCoV-307 tested by Monogram will be presented together with the summary of Study 2019nCoV-312 to evaluate the primary endpoints of Nab response.

Since the Pseudovirus-based Nab response (Wuhan) at 4 different visits including the date of 1st booster dose (Day 1 in 2019nCoV-307), 28 days after 1st booster dose (Day 29 in 2019nCoV-307), date of 2nd booster dose (Day 1 in 2019nCoV-312) and 28 days after 2nd booster dose (Day 29 in 2019nCoV-312) were tested using the similar Pseudovirus Neutralization Assay by two different labs of Monogram and NVX CI, below conversions will be applied to the individual value in the unit of ID50 to the value in the standard unit of IU/mL.

2019nCoV-307 (Monogram): $ID50 * 0.1458 = IU/mL$

2019nCoV-312 (NVX CI): $ID50 * 0.214 = IU/mL$ Pseudovirus-based Nab response (Omicron BA.5) of Study 2019nCoV-312 will be presented including GMT, $GMFR_{Post/Pre}$ and SCR.

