9 CONDUCT OF ANALYSES

The first interim analysis (or called 1st Day 29 primary analysis) will be conducted when all available immunogenicity data (IgG, Nab, and hACE2) and safety data for **the group receiving ancestral strain NVX-CoV2373** through Day 29 have been entered, reviewed, and all queries related to the data have been addressed.

The secondary interim analysis (or called 2nd Day 29 primary analysis) will be performed when all available immunogenicity data (IgG, Nab, and hACE2) and safety data for **the group receiving updated Novavax COVID-19 Vaccine based on recent variant(s)** through Day 29 have been entered, reviewed, and all queries related to the data have been addressed.

The two interim analysis (both Day 29 primary analysis) may be combined depending on the processing of enrollment of participants in the group receiving **ancestral strain NVX-CoV2373** and participants in the group receiving **updated Novavax COVID-19 Vaccine based on recent variant(s)**.

Final analysis will be conducted when all available safety data throughout the study (from Day 1 through EoS) have been entered, reviewed, and all queries related to the data have been addressed.

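### SAP 3.5.2 does not require PP1/PP2 exclusions to be final before, or decided without knowledge of, the Study 312 titers

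*SAP*

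**What the plan says.** The primary endpoint is analysed per protocol (Protocol 9.2.4; SAP 7.2 uses PP1 and PP2). Under SAP 3.5.2, a deviation thought likely to affect the immunogenicity outcomes removes a participant from both sets.

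**Who decides, and when.** Of that exclusion the SAP says: "This determination will be made by the NOVAVAX Clinical Lead prior to database freeze or lock". The next paragraph reads: "When interim analysis (Day 29 primary analysis) DB freezes or Day 181 final analysis DB locks, Syneos will assess protocol deviations" and produces a final consensus file. On the basis of the contractor's listing, "NOVAVAX team will determine whether PDs are major and make the final decision of which participants will be excluded from the PP analysis".

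**On what grounds.** SAP 3.5.2 names general categories: eligibility failure, prohibited therapy, another COVID vaccine and a missed draw. It adds that "laboratory samples obtained sufficiently outside visit windows to likely impact the result will be deemed" major. It also promises: "Criteria for this determination will be established prior to review of PDs". Those criteria are not in the SAP.

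**Where the titers come from.** SAP 7.2.1 says that the Wuhan pseudovirus titers "were tested using the similar Pseudovirus Neutralization Assay by two different labs of Monogram and NVX CI". Study 307 is assigned to Monogram and Study 312 to NVX CI; the SAP abbreviation list expands CI as Clinical Immunology, so this reads as the sponsor's own laboratory.

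**What other analysis remains.** Protocol 9.2.2 allowed immunogenicity to be analysed in the full analysis set as well. SAP 3.2 states that no such analysis will be done.

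**The concern.** The primary claim rests on one paired ratio tested against fixed thresholds, 0.67 and then 1.0, in a single vaccine group. If the person deciding whether a late blood draw is late enough to matter can see that participant's 312/307 ratio, the decision can follow the result, even without intent. The usual protection is to fix the analysis set before the results reach those who define it. The SAP sets a deadline relative to database freeze or lock, but none relative to serology.

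PP2 is not a check on PP1, because SAP 3.5.2 applies the same deviation exclusions to both. With the full-set analysis gone, no planned table shows the ratio with the excluded participants put back.

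**Working it through.** **1. The text side by side**

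| Question | What the plan states | What it leaves open |
|---|---|---|
| Who makes the final decision? | Clinical Lead in one sentence, sponsor team in another (SAP 3.5.2) | Whether either is kept from titers |
| When? | Clinical Lead before freeze or lock; contractor file at freeze or lock (SAP 3.5.2) | Whether before titers are released |
| On what criteria? | General categories; criteria set before deviation review (SAP 3.5.2) | How far out of window counts; the criteria themselves |
| Is there a check afterwards? | Summary and listing of major deviations (SAP 4) | The ratio with excluded participants included |

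**2. The plan's sample size, to confirm the model**

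Inputs from SAP 1.2: SD of the log10 paired ratio 0.61, power 90%, margin 0.67. The two-sided 95% interval gives one-sided 0.025.

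- Formula: n = [SD × (z0.975 + z0.90) / (log10 GMR − log10 0.67)]².
- At a true GMR of 1.0: [0.61 × (1.960 + 1.282) / 0.1739]² = 129.25, so 130 after rounding up. The plan states 129.
- A noncentral-t calculation gives 132 with margin 0.67. With margin 2/3 it gives 129, 85, 62, 49, 40 and 34, which is SAP Table 2 exactly.

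The paired model is therefore the plan's own, and the sample size is not in dispute.

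**3. What result-aware exclusion could do**

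The documents give no number of exclusions, so the following are assumptions: 129 pairs; log10 ratios normal with SD 0.61; true GMR exactly 0.67, so that every pass is a false claim; 0 to 5 exclusions. The rule is that the mean minus t0.975 × s/√n exceeds log10 0.67. There were 40,000 simulated trials per row. In the middle column, 10% of participants (13 of 129) have a deviation at random, and the lowest ratios among those 13 are removed.

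| Exclusions | Ignoring titers | Lowest among the 10% with a deviation | Lowest of all participants (upper bound) |
|---|---|---|---|
| 0 | 0.024 | 0.025 | 0.025 |
| 1 | 0.025 | 0.035 | 0.046 |
| 2 | 0.025 | 0.044 | 0.073 |
| 3 | 0.025 | 0.050 | 0.104 |
| 5 | 0.026 | 0.063 | 0.193 |

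In the middle column, 100 pairs give 0.035 and 0.050 for one and three exclusions; 150 pairs give 0.034 and 0.051.

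**4. Hand check of the middle column**

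- One exclusion multiplies the observed GMR by 1.019 on average. The standard error is 0.61/√128 = 0.0539, so the shift is log10(1.019)/0.0539 = 0.0082/0.0539 = 0.15 standard errors. The upper tail beyond 1.960 − 0.152 = 1.808 is 0.035.
- Three exclusions multiply it by 1.042. The standard error is 0.61/√126 = 0.0543, so the shift is 0.0179/0.0543 = 0.33. The upper tail beyond 1.631 is 0.051, against 0.050 simulated.

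**The case against.** The controls are real. SAP 3.5.1 has deviations reviewed and classified as the study proceeds, ahead of freeze or lock. Some are found by program, including out-of-window draws, and the contractor flags each as major or minor. The Day 29 window is numeric (+4 days), so only the degree of lateness is open. SAP 3.5.2 lists categories and promises criteria before deviation review. SAP 4 commits to a participant listing of major deviations, so these can be audited later. All of this stands, and it confines the discretion mainly to participants with a recorded deviation. But the contractor's flag is only a recommendation, the categories hold only in general, and none of these steps is placed before serology release.

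Four stronger readings are tempting, and the documents do not support them.

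- *That exclusions are decided after the titers have been seen.* SAP 9 requires that immunogenicity and safety data "have been entered, reviewed, and all queries related to the data have been addressed", but as a condition for running the Day 29 analysis. It does not schedule exclusions, and SAP 3.5.1 points to earlier review.
- *That lists may still change after the Day 29 results.* SAP 3.4 names only database lock, and SAP 3.5.2 uses lock for Day 181. But SAP 3.5.1 and 3.5.2 otherwise give freeze or lock together, and the final analysis covers safety only.
- *That open-label treatment is the weakness.* The comparison is within participants, so treatment blinding would not hide a titer. Access to serology is what matters.
- *That the sponsor could drop the lowest ratios at will.* SAP 3.5.2 permits exclusion only for a deviation, so the last column of the table is a bound and not a scenario the plan allows.

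**Conclusion.** The point holds in limited form. The SAP neither requires PP1/PP2 exclusions to be final before the Study 312 titers are known, nor requires the deciders to be unaware of them. The sponsor decides on partly unquantified grounds, two sentences in SAP 3.5.2 do not agree on timing, and no full-set analysis remains to show the effect. Titer-aware decisions are permitted, not prescribed, and nothing in the documents shows that they occur.

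Under the stated assumptions, the possible cost is a one-sided error of about 0.035 with one result-chosen exclusion and about 0.05 with three, twice the nominal 0.025. These figures rest on an assumed 10% deviation rate, assumed exclusion counts and deliberate choice of the lowest ratios. Weaker selection would do less. This is a worthwhile, inexpensive improvement and not a flaw that invalidates the design.

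**What to change.** Amend SAP 3.5.2 and the immunogenicity section as follows:

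1. The PP1 and PP2 exclusion lists, with a reason for each participant, are signed and dated by people without access to Study 312 Day 29 titers or individual 312/307 ratios. This happens before those titers are released to the sponsor study team.
2. Availability of a serology result is applied by program.
3. The two timing sentences in 3.5.2 are reconciled, so that the contractor's final deviation file precedes the sponsor's decision and both precede titer release.
4. A sensitivity analysis of the primary GMR is added in all vaccinated ancestral-strain participants with Day 29 titers from both studies, regardless of deviations.

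The cost is SAP wording, one sign-off, a change in the order of data transfer and one extra table. The downside is that sponsor query resolution on titers waits for the sign-off or is done by the contractor. If the team already works this way, a sentence saying so covers items 1 and 3.

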4 PARTICIPANT DISPOSITION

The number of participants consented, enrolled, and vaccinated will be presented by the study vaccine group for all participants in the Selected Participants Analysis Set.

The number (percentage) of participants in the Selected Participants Analysis Set, Safety Analysis Set, and both PP Analysis Sets who have completed the study from Day 1 through Day 29 for the interim analysis (Day 29 primary analysis) and who have completed the study from Day 1 through EoS for the final analysis will be summarized by the study vaccine group.

The number (percentage) of participants in the Safety Analysis Set who discontinue the study prior to Day 29/EoS and the reason for study discontinuation (eg, AE, death, lost to follow-up, physician/investigator decision, sponsor decision, withdrawal of consent, etc.) will be presented by the study vaccine group. A listing of all participants discontinued from the study will be presented, including the reason for discontinuation and day of last study contact. Day of last study contact will be calculated as follows: date of study discontinuation minus date of Day 1 vaccination + 1. A listing of all screened participants who failed the inclusion/exclusion criteria will also be provided.

The number (percentage) of participants in the Safety Analysis Set with major protocol deviations recorded prior to Day 29/throughout the study will be summarized by the study vaccine group and protocol deviation category (according to the Protocol Deviations and Site Level Non-compliances provided by Syneos and confirmation by NOVAVAX). A listing of all participants with one or more major protocol deviations will also be provided and will include study vaccine group, study day associated with the deviation relative to Day 1, protocol deviation category, and a description of the deviation as recorded by the site.

5 DEMOGRAPHICS AND OTHER BASELINE CHARACTERISTICS

Baseline demographic and background characteristics (eg, age at Day 1 vaccination, self-identified gender, race, ethnicity, height, weight, BMI, child-bearing potential and ECG) will be summarized by the study vaccine group on Safety Analysis Set, and both Per Protocol Sets (PP1 and PP2).

Descriptive statistics (total number of participants [n], mean and standard deviation (SD), median, minimum and maximum values) will be summarized for weight (kg) and height (cm), and derived BMI recorded at Study Day 1. Age (years) at the Day 1 vaccination will be calculated as the closest lower integer result of (Date of Study Day 1 – Date of Birth + 1) / 365.25 and will be summarized using the above descriptive statistics.

The number and percentage of participants for Gender (Male, Female, Other), Ethnicity (Hispanic or Latino, not Hispanic or Latino, not reported), Race (American Indian or Alaska Native, Asian, Black or African American, Native Hawaiian or Other Pacific Islander, White or Caucasian, Not Reported, Other), and BMI category will be summarized.

BMI categories are:

- Underweight: < 18.5
- Healthy: 18.5 – 24.9
- Overweight: 25.0 – 29.9
- Obese: ≥ 30.0

All participants will undergo a baseline ECG at Day 1 prior to study vaccine administration. Baseline ECGs will be read and interpreted by a Central Cardiac Adjudication Committee only as a comparison with new ECG(s) in the event that the participant experiences a cardiac event that constitutes a possible case of myocarditis and/or pericarditis at any time during the study that requires review by the Cardiac Adjudication Committee.

Medical history will be coded using the Medical Dictionary for Regulatory Activities (MedDRA) terms. Baseline medical history recorded at Screening will be summarized by the study vaccine group and by MedDRA System Organ Class/Preferred Term (SOC/PT) for all participants in the Safety Analysis Set. Within each SOC and PT, the number and percentage of participants with at least one medical history event will be presented, respectively. Multiple events within a given SOC and PT for a participant will be counted once.

Physical examination at screening will include height and weight, cervical and axillary lymph nodes, heart, and any other symptom-directed (targeted) examination. Symptom directed (targeted) examination will be performed at unscheduled visits. Diagnoses/abnormalities will be recorded by body system. Physical examination findings will be summarized by study vaccine group and by

body system. Abnormal results will also be summarized as clinically significant or not clinically significant.

The time between Day 1 vaccination dose in Day 307 and Day 1 vaccination dose in Study 312 may be summarized for the study vaccine group using descriptive statistics (ie, mean, median, standard deviation, minimum, maximum).

6 EXTENT OF EXPOSURE

6.1 Study Vaccine

Subject vaccination exposure will be summarized as the number and percentage of participants who received the study vaccine at Day 1 by the study vaccine group.

6.2 Prior and Concomitant Medication and Vaccination

Prior and concomitant medications include recent (\leq 90 days) and current medications, including non-COVID-19 vaccinations. All COVID-19 vaccines administered prior to screening will be recorded in the vaccine history eCRF. After Day 29, all COVID-19 vaccines, and only concomitant medications and other vaccines that have caused or are used to treat an AE will be recorded.

The number (percentage) of participants who record one or more prior/concomitant medications (including vaccines) recorded in the prior/concomitant medications eCRF will be summarized by the study vaccine group and preferred drug name as coded using the WHO drug dictionary for all participants in the Safety Analysis Set. Multiple occurrences of medication usage for a participant will be counted only once within an anatomical therapeutic chemical (ATC) term and standardized medication name.

A by-participant listing of treatment-emergent new concomitant medications (including vaccines) will be presented.

7 ANALYSES ADDRESSING PROTOCOL OBJECTIVES

7.1 Statistical Hypothesis

FoFor To evaluate the Nab responses to ancestral strain Novavax vaccine administered as a second (or subsequent) booster after licensed mRNA vaccines and a first ancestral strain Novavax vaccine booster, two statistical hypotheses will be evaluated in the group receiving **ancestral strain NVX-CoV2373.**

- Non-inferiority of a second (or subsequent) booster dose of NVX-CoV2373, as measured by the lower-bound (LB) of the 95% confidence interval (CI) for $GMR_{312/307}$ defined as the ratio of Nab Geometric Mean Titer (GMT) **28 days after a second (or subsequent) booster dose** of NVX-CoV2373 in Study **2019nCoV-312** versus **28 days after a first booster dose** of NVX-CoV2373 in Study **2019nCoV-307** among the same participants being > 0.67 . This is expressed statistically as:

$$\begin{aligned} H_0: GMR_{312/307} &\leq 0.67 \\ H_1: GMR_{312/307} &> 0.67 \end{aligned}$$

[figure not shown]
- Non-inferiority of a second (or subsequent) booster dose of NVX-CoV2373, as measured by the lower-bound (LB) of the 95% exact CI for the difference of proportion of participants with seroconversion (SCR) in Nab titers **28 days after a second (or subsequent) booster dose** of NVX-CoV2373 in Study **2019nCoV-312** relative to time of Day 1 dose in Study **2019nCoV-307** versus **28 days after a first booster dose** of NVX-CoV2373 in Study **2019nCoV-307** relative to time of Day 1 dose in Study **2019nCoV-307** among the same participants being $> -10\%$. This is expressed statistically as:

$$\begin{aligned} H_0: SCR_{312} - SCR_{307} &\leq -10\% \\ H_1: SCR_{312} - SCR_{307} &> -10\% \end{aligned}$$

Successful demonstration of non-inferiority of the booster dose requires lower-bound (LB) of the 95% confidence interval (CI) for $GMR_{312/307}$ defined as the ratio of Nab Geometric Mean Titer (GMT) **28 days after a second (or subsequent) booster dose** of NVX-CoV2373 in Study **2019nCoV-312** versus **28 days after a first booster dose** of NVX-CoV2373 in Study **2019nCoV-307** among the same participants being > 0.67 to meet the primary endpoint ([Figure 2](#)). If non-inferiority is demonstrated, successful demonstration of superiority being $GMR_{312/307} > 1.0$ will meet the primary endpoint.

Successful demonstration of non-inferiority of the booster dose requires the lower-bound (LB) of the 95% exact CI for the difference of proportion of participants with seroconversion (SCR) in Nab titers **28 days after a second (or subsequent) booster dose** of NVX-CoV2373 in Study **2019nCoV-312** relative to time of Day 1 dose in Study **2019nCoV-307** versus **28 days after a first booster dose** of NVX-CoV2373 in Study **2019nCoV-307** relative to time of Day 1 dose in Study **2019nCoV-307** among the same participants being $> -10\%$ to meet the secondary endpoints.

Figure 2: Geometric Mean Titer and Seroconversion Rate Comparison between 2019nCoV-312 and Study 2019nCoV-307

